11.1.5 Suspected transmission of an infectious agent

For the purposes of reporting, any suspected transmission of an infectious agent via a medicinal product should be considered as an SAE; such cases must be reported immediately, recorded in the AE module of the CRF, and followed as any other SAE. Any organism, virus, or infectious particle (eg, prion protein transmitting transmissible spongiform encephalopathy), pathogenic or nonpathogenic, is considered an infectious agent.

11.1.6 Overdose of investigational medicinal product

Excessive dosing (beyond that prescribed in the protocol and including overdose) should be recorded in the eCRF. Any SAE or nonserious AE associated with excessive dosing must be followed as any other SAE or nonserious AE. These events are only considered AEs or SAEs if there are associated clinical signs and symptoms or if the act of taking the excess medicine itself is an AE or SAE (eg, suicide attempt).

11.1.7 Safety signal detection

Selected data from this study will be reviewed periodically to detect as early as possible any safety concern(s) related to the IMP so that Investigators, clinical study subjects, regulatory authorities, and IRBs/IECs will be informed appropriately and as early as possible.

The Study Physician or medically qualified designee/equivalent will conduct an ongoing review of SAEs and perform ongoing SAE reconciliations in collaboration with the PS representative.

As appropriate for the stage of development and accumulated experience with the IMP, medically qualified personnel at UCB may identify additional safety measures (eg, AEs, vital signs, laboratory, ECG, and echocardiogram results) for which data will be periodically reviewed during the course of the study.

In addition, an unblinded independent DMC will oversee safety data approximately every 6 months (subject to DMC recommendation) during the course of the study during which the safety of PSL will be assessed. The safety variables and the decision rules to be used will be specified in the DMC charter. This analysis will inform any decisions regarding changes in study conduct and/or study termination. The precise membership, scope, and responsibilities of the DMC are described in the DMC charter.

11.2 Laboratory measurements

Laboratory assessments will be conducted using standard methods at a central laboratory. The central laboratory will provide the Investigator with dedicated, standardized sampling equipment (labels, needles, tubes), and a study-specific Laboratory Manual, which will explain how to use the equipment and how to ship the samples to the central laboratory. The laboratory parameters measured are presented in [Table 11-2](#).

The total blood volume drawn for clinical laboratory assessments per subject will be a maximum of 31.6mL by sampling, which includes 2mL for hematology, 5mL for blood chemistry, 5mL and 20 μ L for AED and PSL plasma level (including back-up samples for AED assay), 6mL for genetic substudy, 13.5mL for genomic assessments, and 80 μ L for PK measurements.

Table 11–2: Laboratory measurements

Hematology	Chemistry	Urinalysis
Basophils	ALP	Glucose
Eosinophils	ALT	pH
Hematocrit	AST	RBC
Hemoglobin	Bilirubin	Total protein
Lymphocytes	BUN or urea	WBC
MCH	Calcium	Microscopy (WBC, RBC ^a , casts, crystals, bacteria)
MCHC	Chloride	Other
MCV	Creatinine	FSH ^b
Monocytes	Glucose	
Neutrophils	HDL	
Platelet count	LDH	
RBC count	LDL	
WBC count	Magnesium	
	Potassium	
	Sodium	
	Total bilirubin	
	Total cholesterol	

ALP=alkaline phosphatase; ALT=alanine aminotransferase; AST=aspartate aminotransferase; BUN=blood urea nitrogen; HDL=high density lipoprotein; FSH=follicle stimulating hormone; LDH=lactate dehydrogenase; LDL=low density lipoprotein; MCH=mean corpuscular hemoglobin; MCHC=mean corpuscular hemoglobin concentration; MCV=mean corpuscular volume; RBC=red blood cell; WBC=white blood cell

^a Microscopy will be performed only in case of abnormalities.

^b Only applicable to postmenopausal women

Where applicable (ie, for women of childbearing potential), a serum pregnancy test (β -human chorionic gonadotropin levels) will be conducted at Visits 1 and 7 only. Urine pregnancy test will be used at other visits. If pregnancy is suspected at any time during the study, an interim test should be performed.

Women not agreeing to use birth control must be abstinent or be of nonchildbearing potential, defined as being postmenopausal (for at least 2 years before the Screening Visit [Visit 1]), verified by serum follicle stimulating hormone level >40mIU/mL at the Screening Visit (Visit 1), or permanently sterilized (eg, bilateral tubal occlusion, hysterectomy, bilateral salpingectomy), or congenitally sterile.

Sampling time and last AED intake should be recorded in the eCRF.

11.2.1 Evaluation of PDILI

The PDILI IMP discontinuation criteria for this study are provided in [Section 6.3.1](#), with the accompanying required follow-up investigation and monitoring detailed below. All PDILI events must be reported as an AE and reported to the study site and Sponsor within 24 hours of learning of their occurrence. Any PDILI event that meets the criterion for potential Hy's Law must be reported as an AE of special interest (see [Section 11.1.1.2.2](#)), and, if applicable, also reported as an SAE (see [Section 11.1.1.2](#)).

Evaluation of PDILI consists of the diagnostic testing and continued monitoring included in [Table 11-3](#) (specific tests dependent on laboratory results and corresponding symptoms) and consultation with a local hepatologist (if applicable; discussed in [Section 11.2.1.1](#)). The local hepatologist is the expert usually consulted by the treating physician for assessment and management of potential hepatic disease. This would usually be a hepatologist, but may be a gastroenterologist. Additional investigation and monitoring may be required and adapted based on the diagnosis after the cause of the liver injury/abnormality is confirmed (details in [Section 11.2.1.4](#)).

The results of all monitoring, including laboratory testing and other testing, should be made available to the study site and Sponsor.

All initial tests resulting in abnormal hepatic laboratory values need to be repeated, but appropriate medical action must not be delayed waiting for the repeat result.

If tests are done locally for more rapid results, a concurrent sample should also be sent to the central laboratory whenever possible. Medical care decisions are to be made initially using the most rapidly available results and a conservative approach must be taken if the results from the 2 laboratory tests are significantly different. Data from the local and central laboratory are to be recorded on the applicable eCRF pages.

When IMP is discontinued, all concomitant medications and herbal supplements that are not medically necessary should also be discontinued. In these cases, the Investigator should also consider dose reduction for medically necessary concomitant medication and consider changing any medically required concomitant medication known to be hepatotoxic to a suitable alternative.

When IMP is stopped due to PDILI (as described in [Section 6.3.1](#)), IMP must be permanently discontinued unless a subsequent alternative diagnosis fully explains the hepatic findings. If a subsequent alternative diagnosis fully explains the hepatic findings, and the requirements provided in [Section 11.2.1.2.1](#) are met, rechallenge with IMP may be appropriate after discussion with the Sponsor.

Rechallenge with a substance potentially causing drug-induced liver injury is dangerous, may be fatal, and must not occur.

The approach to investigate PDILI is summarized in [Table 11-3](#).

Table 11-3: Required investigations and follow up for PDILI

Laboratory value			Immediate		Follow up	
ALT or AST	Total bilirubin	Symptoms ^a of hepatitis or hypersensitivity	Consultation requirements	Actions	Testing	Evaluation
≥3xULN	≥2xULN ^b	NA	Hepatology consult. ^c	Immediate, permanent IMP discontinuation.	Essential: Must have repeat liver chemistry values and additional testing completed ASAP (see Section 11.2.1.3); recommended to occur at the site with HCP.	Monitoring of liver chemistry values at least twice per week until values normalize, stabilize, or return to within Baseline values. ^d
≥8xULN	NA	Medical Monitor must be notified within 24 hours (eg, by laboratory alert) and subject discussed with Medical Monitor ASAP.				
≥3xULN	NA	Yes	Immediate, temporary or permanent, IMP discontinuation.			
≥3xULN (and ≥2x Baseline) and <5xULN	<2xULN	No	Discussion with Medical Monitor required if the criterion that allows for IMP continuation is met.	Further investigation immediate IMP discontinuation not required (see Section 11.2.1.2).	Not required unless otherwise medically indicated (at discretion of Investigator).	
≥5xULN (and ≥2x Baseline)	<2xULN	No	Discussion with Medical Monitor required.	Immediate, permanent IMP discontinuation.	Essential: Every attempt must be made to have repeat liver chemistry values and additional testing completed within 48 hours at the site with HCP (see Section 11.2.1.3).	Monitoring of liver chemistry values at least twice per week until values normalize, stabilize, or return to within Baseline values. ^d

ALP=alkaline phosphatase; ALT=alanine aminotransferase; ASAP=as soon as possible; AST=aspartate aminotransferase; HCP=healthcare practitioner; IMP=investigational medicinal product; NA=not applicable; PDILI=potential drug-induced liver injury; ULN=upper limit of normal

-
- ^a Hepatitis symptoms include fatigue, nausea, vomiting, and right upper quadrant pain or tenderness; hypersensitivity symptoms include eosinophilia (>5%), rash, and fever (without clear alternative cause).
- ^b If the subject also has $\geq 2 \times$ ULN ALP, the possibility of an indication of biliary obstruction should be discussed with the Medical Monitor.
- ^c Details provided in [Section 11.2.1.1](#). The local hepatologist is the expert usually consulted by the treating physician for assessment and management of potential hepatic disease. This would usually be a hepatologist, but may be a gastroenterologist.
- ^d Unless an alternative monitoring schedule is agreed by the Investigator and UCB Study Physician. Determination of stabilization is at the discretion of the Investigator in consultation with the hepatologist (as applicable) and UCB Study Physician, as needed.

REDACTED COPY
This document cannot be used to support any marketing authorization application and any extensions or variations thereof.

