6.3.1 Potential drug-induced liver injury IMP discontinuation criteria

Subjects with potential drug-induced liver injury (PDILI) must be assessed to determine if IMP must be discontinued. In addition, all concomitant medications and herbal supplements that are not medically necessary should also be discontinued.

The PDILI criteria below require immediate and permanent discontinuation of IMP:

- Subjects with either of the following:
 - ALT or AST $\geq 5\text{x ULN}$
 - ALT or AST $\geq 3\text{xULN}$ and coexisting total bilirubin $\geq 2\text{xULN}$

The PDILI criterion below requires immediate discontinuation of IMP:

- Subjects with ALT or AST $\geq 3\text{xULN}$ who exhibit temporally associated symptoms of hepatitis or hypersensitivity. Hepatitis symptoms include fatigue, nausea, vomiting, right upper quadrant pain or tenderness. Hypersensitivity symptoms include fever (without clear alternative cause), rash, or eosinophilia (ie, $>5\%$).

The PDILI criterion below allows for subjects to continue on IMP at the discretion of the Investigator:

- Subjects with ALT or AST $\geq 3\text{xULN}$ (and $\geq 2\text{x Baseline}$) and $< 5\text{xULN}$, total bilirubin $< 2\text{xULN}$, and no eosinophilia (ie, $\leq 5\%$), with no fever, rash, or symptoms of hepatitis (eg, fatigue, nausea, vomiting, right upper quadrant pain or tenderness).

Evaluation of PDILI must be initiated as described in [Section 11.2.1](#). If subjects are unable to comply with the applicable monitoring schedule, IMP must be discontinued immediately.

Investigators should attempt to obtain information on subjects in the case of IMP discontinuation to complete the final evaluation. Subjects with PDILI should not be withdrawn from the study until investigation and monitoring are complete. All results of these evaluations and observations, as well as the reason(s) for IMP discontinuation and subject withdrawal (if applicable), must be recorded in the source documents. The eCRF must document the primary reason for IMP discontinuation.

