11.2.1.2 Immediate action: determination of IMP discontinuation

All PDILI events require immediate action, testing, and monitoring.

The immediate action is dependent on the laboratory values and symptoms of hepatitis or hypersensitivity and ranges from continuation of IMP (followed by immediate investigation) to immediate and permanent discontinuation (see [Section 6.3.1](#) and [Table 11-3](#) for details).

When IMP is discontinued, all concomitant medications and herbal supplements that are not medically necessary should also be discontinued. The Investigator should also consider dose reduction for medically necessary concomitant medication and consider changing any medically required concomitant medication known to be hepatotoxic to a suitable alternative.

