11.2.1.2.1 IMP restart/rechallenge (if applicable)

Rechallenge with a substance potentially causing drug-induced liver injury is dangerous, may be fatal, and must not occur.

Subjects who are immediately discontinued from IMP due to having met certain criteria for PDILI (as described in [Section 6.3.1](#) and [Table 11-3](#)), but for whom an alternative diagnosis is confirmed, can rarely restart IMP. Rechallenge with IMP can occur only if ALL of the following requirements are met:

- The results of additional testing and monitoring described in [Section 11.2.1.3](#) and [Section 11.2.1.4](#) confirm a nondrug-related cause for the abnormal hepatic laboratory parameters and any associated symptoms (ie, a subsequent alternative diagnosis fully explains the hepatic findings).
- No alternative treatment options are available to the subject.
- The subject has shown clear therapeutic benefit from the IMP.
- Subject's ALT or AST elevations do not exceed $\geq 3xULN$.
- Subject's total bilirubin is $< 1.5xULN$.
- Subject has no signs or symptoms of hypersensitivity.
- The rechallenge is approved by the UCB responsible physician, DMC, and a hepatologist. The hepatologist must be external to UCB but may be a member of the DMC. It is recommended that the hepatologist be a local hepatology expert or the hepatologist treating the subject.
- Subject agrees to the Investigator-recommended monitoring plan.

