### 10.3.1 Subjects with potential drug-induced liver injury (PDILI)

There are specific criteria described in the protocol Section 11 to evaluate subjects for potential drug-induced liver injury (PDILI). The evaluations required by protocol for PDILI subjects are collected on the following CRFs:

- Most Recent Study Medication Administration, for PDILI
- Laboratory Tests DILI
- Vital Signs DILI
- Hepatic Event Supplemental Medical History for PDILI
- Potential Hepato-Toxic Medications Inquiry for PDILI

- Symptoms of Hepatitis and Hypersensitivity for PDILI
- Lifestyle PDILI
- Family Medical History for PDILI

Listings will be prepared presenting subjects with PDILI data. A summary of number and percent of subjects meeting PDILI criteria (ALT, AST, total bilirubin, ALP, and presence of symptoms) during the Treatment Period (scheduled and unscheduled visits) will be provided following the UCB standard table shell for PDILI Data. Subjects who met these criteria will be listed.

ALT Criteria	AST Criteria	Total Bilirubin Criteria	ALP Criteria	Presence of Symptoms
≥3xULN	≥3xULN	≥2xULN	≥2xULN	NA
≥8xULN	≥8xULN	NA		NA
≥3xULN	≥3xULN	NA		Y
≥3xULN <-5xULN and ≥2x Baseline	≥3xULN <-5xULN and ≥2xBaseline	<2xULN		N
≥5xULN <-8xULN and ≥2x Baseline	≥5xULN <-8xULN and ≥2xBaseline	<2xULN		N
≥5xULN and ≥2xBaseline	≥5xULN and ≥2xBaseline	<2xULN		N

N=No; NA=Not Applicable; ULN= upper limit of normal; Y=Yes.

A summary table highlighting the potential cases of Hy's Law, within each treatment group will be presented. Hy's Law is defined as:

- AST ≥3xULN or ALT ≥3xULN and
- Total Bilirubin ≥2xULN

In order to meet the above criteria, a subject must experience the elevation in bilirubin and ALT or AST at the same visit. For example, a subject who experiences a ≥2 x ULN elevation of bilirubin at one visit and a 3 x ULN elevation in ALT (or AST) at a subsequent visit has not fulfilled the Hy's law criteria.

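### For ALT/AST 5 to <8xULN with symptoms and bilirubin <2xULN, Protocol Table 11-3 allows a temporary stop of study drug where Section 6.3.1 requires a permanent one

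*Protocol*

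**What the plan says.** Protocol Section 6.3.1 sorts the liver criteria into three groups. The first group opens with "The PDILI criteria below require immediate and permanent discontinuation of IMP" and contains two criteria: ALT or AST at least 5xULN, and ALT or AST at least 3xULN with total bilirubin at least 2xULN. The 5xULN criterion carries no condition on symptoms, bilirubin or baseline. The second group is ALT or AST at least 3xULN with symptoms, with no upper limit; it requires an immediate stop but is not called permanent. The third group, 3 to <5xULN without symptoms and with low bilirubin, lets the investigator continue treatment.

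Table 11-3 in Section 11.2.1 sets out the same ground by row. The row for at least 5xULN (and at least twice Baseline) applies when bilirubin is below 2xULN and symptoms are absent; its action is immediate and permanent. The row for at least 3xULN with symptoms, any bilirubin, has no upper limit, and its action is "Immediate, temporary or permanent, IMP discontinuation".

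Three other places bear on which text governs. Section 11.2.1 opens with "The PDILI IMP discontinuation criteria for this study are provided in" and points to Section 6.3.1. Later in that section, for a stop due to liver injury, it says "IMP must be permanently discontinued unless a subsequent alternative diagnosis fully explains the hepatic findings". Section 11.2.1.2 begins "The immediate action is dependent on the laboratory values and symptoms of hepatitis or hypersensitivity" and refers the reader to Section 6.3.1 and Table 11-3 together. On restart, Section 11.2.1.2.1 starts with "Subjects who are immediately discontinued from IMP due to having met certain criteria for PDILI", cites both sources, and does not say which criteria are meant.

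**The concern.** The protocol uses the word permanent deliberately: both Section 6.3.1 and Table 11-3 separate permanent stops from stops that need not be permanent. The two sources put the same subject on opposite sides of that line.

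The direction is also wrong. Adding symptoms to a given enzyme elevation should never make a hepatic stopping rule read as looser, and here it does. The symptom switch is easily tripped. Footnote a of Table 11-3 counts fatigue as a hepatitis symptom, and Section 2.3.1 lists fatigue among the most frequent adverse events on padsevonil. Section 6.3.1 asks that symptoms be temporally associated, but the table column is a plain yes or no.

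At stake is eligibility for restart. Section 11.2.1.2.1 warns that rechallenge with a causal drug may be fatal, yet whether this subject can enter that process depends on which text the site reads.

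**Working it through.** No sample size or error rate is involved. The check places each enzyme band, with and without symptoms, on both texts.

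**Inputs**
- Section 6.3.1: at least 5xULN is permanent, unconditionally; at least 3xULN with symptoms is immediate.
- Table 11-3: five rows, namely at least 3xULN with bilirubin at least 2xULN; at least 8xULN; at least 3xULN with symptoms; 3 to <5xULN without symptoms; at least 5xULN without symptoms. The action for at least 8xULN is read from the merged permanent cell above it.

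**Bilirubin below 2xULN, and ALT or AST at least twice Baseline**

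| ALT or AST | Symptoms | Section 6.3.1 | Table 11-3 | Agree? |
|---|---|---|---|---|
| 3 to <5xULN | No | May continue | May continue | Yes |
| 3 to <5xULN | Yes | Immediate stop | Temporary or permanent stop | Compatible |
| 5 to <8xULN | No | Permanent stop | Permanent stop | Yes |
| 5 to <8xULN | Yes | Permanent stop | Temporary or permanent stop | **No** |
| >=8xULN | No | Permanent stop | Permanent stop | Yes |
| >=8xULN | Yes | Permanent stop | Permanent stop (the symptomatic row also fits) | Yes |

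One cell of six conflicts.

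**Worked case.** ALT 6xULN, bilirubin 1xULN, Baseline 1xULN.
- No symptoms: both texts require a permanent stop.
- Symptoms: Section 6.3.1 still requires a permanent stop. In the table, the 5xULN row is excluded because it needs symptoms to be absent, the 8xULN row because 6 < 8, and the bilirubin row because 1 < 2. Only the symptomatic row is left.

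**Are the row limits as read?** SAP Section 10.3.1 plans "A summary of number and percent of subjects meeting PDILI criteria" and tabulates the criteria again. There too the symptomatic row at 3xULN has no upper bound, and both rows starting at 5xULN are restricted to subjects without symptoms. The SAP table has no action column, so it confirms the limits but not the actions.

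**The Baseline condition in the 5xULN row.** A value of 5xULN is at least twice Baseline only if Baseline is at most 5/2 = 2.5xULN. Exclusion criterion 3 removes values above 2.0xULN at screening, but SAP Section 3.3.2 takes Baseline as the last pre-dose value, which can be the Visit 2 sample, so a higher Baseline is possible. If Baseline is 2.6xULN, twice Baseline is 5.2xULN. An ALT of 5.1xULN without symptoms then misses the 5xULN row and is too high for the <5xULN row, so no row fits, while Section 6.3.1 still requires a permanent stop. This is a gap in the table, not a second contradictory instruction, but the repair has to close it. If the symptomatic row were capped at 5xULN and the Baseline condition kept, a symptomatic subject at 5.1xULN would also fit no row.

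**The case against.** The best reply is that the protocol already settles the matter. Section 11.2.1 names Section 6.3.1 as the home of the stopping criteria, and Table 11-3 is titled as investigations and follow-up. A permanent stop satisfies both texts, so no investigator is forced to breach either. The rule that a stop is permanent unless another diagnosis fully explains the findings covers every liver-related stop. Restart needs every condition in Section 11.2.1.2.1, including approval by the sponsor's physician, the DMC and an external hepatologist. Overlapping criteria exist elsewhere in the scheme and make sense only if the strictest applies. The merged cells may also give symptomatic subjects a stricter consultation and testing pathway, so calling the table looser rests on one cell. The Baseline gap is remote. On this view the point is editorial.

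Much of this stands as a limit on consequences, and it rules out a claim of serious hazard. It does not remove the conflict. Section 11.2.1.2 sends the reader to both sources without ranking them, and no text says the stricter one prevails. A strictest-row reading works inside the table at 8xULN and above, where a permanent row also fits. It fails at 5 to <8xULN, where the symptomatic row is the only one that fits. The alternative-diagnosis rule applies equally to all liver stops, so it cannot reconcile two classifications of the same subject. The restart section relies on unnamed criteria from both sources, which is where the difference shows.

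**Conclusion.** The concern holds: Table 11-3 is wrong as written for one group, ALT or AST 5 to <8xULN with symptoms and bilirubin below 2xULN. It should be corrected, but the practical effect is limited. Study drug stops immediately under either text, the Medical Monitor is involved (Section 11.2.1.1), and restart is tightly gated. What remains open is whether such a subject may be considered for restart.

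The documents give no expected number of these subjects among the 400 to be randomised; few are likely. No efficacy analysis is affected. The conclusion rests on reading the symptomatic row's action text as belonging to that row, which its distinct wording supports, and on row limits that the SAP repeats. It does not depend on the Baseline example, which matters only for how the table is repaired.

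**What to change.** In Protocol Table 11-3:
- Bound the symptomatic row at 3 to <5xULN.
- Make the immediate, permanent row at 5xULN or more apply with or without symptoms.
- Delete the twice-Baseline condition from that row, since Section 6.3.1 has none at this level.
- Keep the hepatology consultation and urgent testing for symptomatic subjects wherever the merged cells assign them.

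In Section 11.2.1.2.1, add one sentence naming the criteria after which restart may be considered.

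The cost is two row labels and one sentence at the next amendment, with a note to the approximately 200 sites. No new procedure is needed. The SAP Section 10.3.1 table can be aligned at the same time so that its categories match; this is optional, because that table assigns no action.
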